During Cohorts B–D, an IMC will provide additional safety oversight for cohorts evaluating regimens with AT-527 doses higher than 550 mg BID. The IMC will include representatives from Clinical Science and Clinical Safety who are independent of the Sponsor study team and a Biostatistician who does not have regular contact with the sites. In addition to the ongoing assessment of the incidence, nature, and severity of adverse events, serious adverse events, deaths, and vital sign and laboratory abnormalities performed by the Medical Monitor, the IMC will review safety data through Day 10 for the first 20 patients enrolled in those cohorts.

The IMC will pause further enrollment in the study to conduct a comprehensive safety assessment of all cumulative data if any of the following criteria are met.

- Death in any patient for which the cause of death is judged by the investigator to have a reasonable possibility of relatedness to the study drug
- Occurrence in any patient of a life-threatening serious adverse event for which the causal relationship is judged by the investigator to have a reasonable possibility of relatedness to the study drug
- > 20% of the enrolled patients in any cohort experience clinically significant Grade 3 or 4 adverse events judged by the investigator to have a reasonable possibility of relatedness to the study drug

The IMC will make recommendations as to the further conduct of the study as outlined in the IMC Charter. Other specific operational details such as the IMC's composition, frequency and timing of meetings, and members' roles and responsibilities will be detailed in the IMC Charter. *Cohorts evaluating regimens with AT-527 doses lower than a previously tested dose regimen will not require additional IMC oversight..*

Number of Patients

Up to approximately 404 non-hospitalized adult patients with mild or moderate COVID-19 will be enrolled in this study.

Target Population

Inclusion Criteria

Patients must meet the following criteria for study entry:

- Signed Informed Consent Form
- Age ≥ 18 years at time of signing Informed Consent Form
- Willing and able to comply with the study protocol and all study procedures, in the opinion of the investigator
- Positive SARS-CoV-2 diagnostic test (reverse transcription polymerase chain reaction [RT-PCR] or rapid antigen test) at screening
- Has symptoms consistent with mild or moderate COVID-19, as determined by the investigator, with onset ≤ 5 days prior to randomization

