3. STUDY DESIGN

3.1 DESCRIPTION OF THE STUDY

This is a Phase II, randomized, double-blind, placebo-controlled study to evaluate the antiviral activity, safety, pharmacokinetics, and efficacy of selected dose regimens of AT-527 compared with placebo in non-hospitalized adult patients with mild or moderate COVID-19. If all potential cohorts are fully enrolled, the study will enroll up to approximately 404 patients globally.

Patients will be screened up to 72 hours prior to randomization. Patients who do not meet the criteria for participation in this study (screen failure) cannot be re-screened. The investigator will record reasons for screen failure in the screening log.

Eligible patients will be enrolled sequentially into one of up to five possible treatment cohorts (Cohorts A–E). Sixty patients will be enrolled into Cohort A; Cohorts B–D will enroll 40 patients each, *and Cohort E will enroll approximately 224 patients.*

Patients who withdraw from the study or who discontinue study treatment will not be replaced. However, patients who withdraw from the study after screening, but before receiving the first dose, will be replaced.

In Cohort A, patients will be randomized in a 1:1 ratio to receive either AT-527 550 mg (or placebo) BID on Days 1–5, with assessment visits on Days 3, 5, and 7. After 30 patients (50% enrollment) in Cohort A have completed assessments through Day 10, an interim review of safety data will be conducted to determine the AT-527 dose and regimen for Cohort B.

In Cohorts B–D, patients will be randomized in a 3:1 ratio to receive either AT-527 or placebo on Days 1–5, with assessment visits on Days 3, 5 and 7. Dose regimen decisions for Cohorts C–D will be made by the Sponsor study team following unblinded review of safety data by an Internal Monitoring Committee (IMC) after 20 patients (approximately 15 active and 5 placebo) enrolled in the previous cohort have completed assessments through Day 10. The maximum dose to be tested in the study will not exceed AT-527 1100 mg BID for 5 days. Depending on emerging data, the Sponsor may also evaluate regimens with doses of AT-527 lower than 550 mg BID. *Cohorts that evaluate regimens with AT-527 doses lower than a previously tested dose regimen will not require IMC oversight.*

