In Cohort E, patients will be randomized in a 1:1 ratio to receive either AT-527 (or placebo) BID on Days 1–5, with assessment visits on Days 3, 5, 7 and 14. Cohort E may be initiated prior to the completion of all four prior cohorts, and will utilize a dose regimen selected from a previous cohort. As Cohort E dose regimen will have been previously tested, this cohort does not require an IMC.

For all cohorts, visits may be conducted in clinic or by mobile nursing. Where local policies and local site logistics permit, patients may also be confined in clinic during Days 1–7. Where treatment occurs in the inpatient setting, the purpose of hospitalization must not be for severe COVID-19 requiring inpatient treatment. An end of study safety follow-up telephone call on Day 33. The total study duration for each patient will be 33 days.

For all cohorts, a selection of different samples will be collected to assess SARS-CoV-2 viral status at various timepoints. To evaluate the PK properties of AT-527, PK samples will be collected at various timepoints. Patients will be closely monitored for COVID-19 signs and symptoms and adverse events; adverse events will be graded according to National Cancer Institute Common Terminology Criteria for Adverse Events (NCI CTCAE) v5.0.

During Cohorts B–D, an IMC will provide additional safety oversight for cohorts evaluating regimens with AT-527 doses higher than 550 mg BID. The IMC will include representatives from Clinical Science and Clinical Safety who are independent of the Sponsor study team, and a Biostatistician who does not have regular contact with the sites. In addition to the ongoing assessment of the incidence, nature, and severity of adverse events, serious adverse events, deaths, and vital sign and laboratory abnormalities performed by the Medical Monitor, the IMC will review safety data through Day 10 for the first 20 patients enrolled in those cohorts.

[figure not shown]
The IMC will pause further enrollment in the study to conduct a comprehensive safety assessment of all cumulative data if any of the following criteria are met.

- Death in any patient for which the cause of death is judged by the investigator to have a reasonable possibility of relatedness to the study drug
- Occurrence in any patient of a life-threatening serious adverse event for which the causal relationship is judged by the investigator to have a reasonable possibility of relatedness to the study drug

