- >20% of the enrolled patients in any cohort experience clinically significant Grade 3 or 4 adverse events judged by the investigator to have a reasonable possibility of relatedness to the study drug

The IMC will make recommendations as to the further conduct of the study as outlined in the IMC Charter. Other specific operational details such as the IMC's composition, frequency and timing of meetings, and members' roles and responsibilities will be detailed in the IMC Charter. *Cohorts evaluating regimens with AT-527 doses lower than a previously tested dose regimen will not require additional IMC oversight..*

[Figure 1](#) presents an overview of the study design. Schedule of activities are provided in [Appendix 1](#), [Appendix 2](#), and [Appendix 3](#).

Figure 1 Study Schema

BID=twice a day; COVID-19=coronavirus disease 2019; IA=Interim Analysis; IMC=Internal Monitoring Committee; PBO=placebo; PO=orally; R=randomization; SARS-CoV-2=severe acute respiratory syndrome coronavirus-2.

Note: Patients in Cohort A and Cohort E will be randomized in a 1:1 ratio (AT-527:placebo). Cohorts B–D will be randomized in a 3:1 ratio (AT-527:placebo).

^a Planned interim safety analysis after the first 30 patients enrolled have completed assessments through Day 10 will inform dose regimen decision for Cohort B.

^b Cohorts evaluating regimens with AT-527 doses lower than a previously tested dose regimen will not require additional IMC oversight.

^c Cohort E will utilize a dose regimen selected from a previous cohort and may be initiated prior to the completion of all four prior cohorts.

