4.2.2 Blinding

Study site personnel and patients will be blinded to treatment assignment during the study. Following interim analyses, the Sponsor study team and appropriate senior management personnel will be unblinded at a treatment group level, however the Sponsor and its agents will be blinded to individual treatment assignment, with the exception of individuals who require access to patient treatment assignments to fulfill their job roles during a clinical trial. These roles include the unblinding group responsible, clinical supply chain managers, sample handling staff, operational assay group personnel, IxRS service provider, and IMC members. Supporting biometrics staff will have access to the unblinded data to allow for data transfer, unblinding, and summarizing of *interim analyses* and IMC review.

While PK samples must be collected from patients assigned to the placebo arm to maintain the blinding of treatment assignment, PK assay results for these patients are generally not needed for the safe conduct or proper interpretation of the study data. Laboratories responsible for performing study drug PK assays will be unblinded to patient treatment assignments to identify appropriate samples for analysis. PK samples from patients assigned to the placebo arm will not be analyzed for study drug PK concentration except by request (e.g., to evaluate a possible error in dosing).

If unblinding is necessary for a medical emergency (e.g., in the case of a serious adverse event for which patient management might be affected by knowledge of treatment assignment), the investigator will be able to break the treatment code by contacting the IxRS. The treatment code should not be broken except in emergency situations. The investigator is not required to contact the Medical Monitor prior to breaking the treatment code. However, the investigator should contact the Medical Monitor to discuss emergency unblinding after the treatment code has been broken.

If the investigator wishes to know the identity of the study drug for any reason other than a medical emergency, he or she should contact the Medical Monitor directly. The

investigator should document and provide an explanation for any non-emergency unblinding. If the Medical Monitor agrees to patient unblinding, the investigator will be able to break the treatment code by contacting the IxRS.

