5.1.1 Risks Associated with AT-527

AT-527 has been evaluated in two completed clinical studies (AT-01B-001 and AT-01B-002) in healthy volunteers and HCV-infected patients. In the first study, 88 subjects were dosed with blinded study drug (AT-527 or placebo), with 72 of the 88 subjects receiving active study drug. AT-527 was well-tolerated in both healthy volunteers and HCV-infected patients as either single or multiple doses (seven daily doses) up to 600 mg of AT-527 (equivalent to 553 mg AT-511 free base). In the second study, 10 HCV-infected patients received AT-527 550 mg in combination with 60 mg daclatasvir QD for 8-12 weeks. There were no serious adverse events, dose-limiting toxicities, or premature discontinuations.

In the COVID-19 development program, AT-527 is being evaluated in one Phase I study (AT-03A-002) in healthy volunteers and two Phase II studies in COVID-19 patients (AT-03A-001 and WV43042). In the ongoing study AT-03A-002, the completed Cohorts 1 and 3 investigated AT-527 doses at 550 mg (as 1 × 550 mg tablet) or placebo BID for 5 days and 825 mg (as 3 × 275 mg) or placebo BID for 10 days, respectively. The completed Cohort 2 investigated a single dose of 550 mg (as 2 × 275 mg tablets). Preliminary safety data from 41 subjects in the completed Cohorts 1–3 show no premature discontinuations due to AT-527-related AEs, no SAEs, and no patterns with regards to laboratory-, ECG-, or vital sign abnormalities. In the ongoing study AT-03A-001, AT-527 is being evaluated at a dose of 550 mg BID in hospitalized patients with moderate COVID-19 and risk factors for poor outcomes. Preliminary results from an interim analysis performed after the first 70 patients show that AT-527 was generally well tolerated. There were no drug-related SAEs. Non-serious AEs were equally distributed across treatment arms. Most were mild-to-moderate in severity and assessed as not related to the study drug. No safety concerns or newly determined risks were identified. (see further detail in Section 1.2 and 1.3).

In the current study (WV43042), a planned interim safety analysis after the first 30 patients enrolled in Cohort A (dosed at 550 mg BID for 5 days) had completed assessments through Day 10, identified no safety concerns. All AEs were Grade 1 or 2 in severity and no SAEs were reported.

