5.3.4 Assessment of Causality of Adverse Events

Investigators should use their knowledge of the patient, the circumstances surrounding the event, and an evaluation of any potential alternative causes to determine whether an adverse event is considered to be related to the study drug, indicating "yes" or "no" accordingly. The following guidance should be taken into consideration (see also [Table 4](#)):

- Temporal relationship of event onset to the initiation of study drug
- Course of the event, with special consideration of the effects of dose reduction, discontinuation of study drug, or reintroduction of study drug (as applicable)
- Known association of the event with the study drug or with similar treatments
- Known association of the event with the disease under study
- Presence of risk factors in the patient or use of concomitant medications known to increase the occurrence of the event
- Presence of non-treatment-related factors that are known to be associated with the occurrence of the event

Table 4 Causal Attribution Guidance

Is the adverse event suspected to be caused by the study drug on the basis of facts, evidence, science-based rationales, and clinical judgment?	
YES	There is a plausible temporal relationship between the onset of the adverse event and administration of the study drug, and the adverse event cannot be readily explained by the patient's clinical state, intercurrent illness, or concomitant therapies; and/or the adverse event follows a known pattern of response to the study drug; and/or the adverse event abates or resolves upon discontinuation of the study drug or dose reduction and, if applicable, reappears upon re-challenge.
NO	An adverse event will be considered related, unless it fulfills the criteria specified below. Evidence exists that the adverse event has an etiology other than the study drug (e.g., preexisting medical condition, underlying disease, intercurrent illness, or concomitant medication); and/or the adverse event has no plausible temporal relationship to administration of the study drug (e.g., cancer diagnosed 2 days after first dose of study drug).

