1.2.2 Data Monitoring

During Cohorts B–E, an IMC will provide additional safety oversight for cohorts evaluating regimens with AT-527 doses higher than 550 mg BID. The IMC will include representatives from Clinical Science and Clinical Safety who are independent of the Sponsor study team, and a Biostatistician who does not have regular contact with the sites. In addition to the ongoing assessment of the incidence, nature, and severity of AEs, SAEs, deaths, and vital signs and laboratory abnormalities performed by the

Medical Monitor, the IMC will review safety data through Day 10 for the first 20 patients enrolled in those cohorts.

The IMC will pause further enrollment in the study to conduct a comprehensive safety assessment of all cumulative data if any of the following criteria are met:

- Death in any patient for which the cause of death is judged by the investigator to have a reasonable possibility of relatedness to the study drug
- Occurrence in any patient of a life-threatening SAE for which the causal relationship is judged by the investigator to have a reasonable possibility of relatedness to the study drug
- Greater than 20% of the enrolled patients in any cohort experience clinically significant Grade 3 or 4 AEs judged by the investigator to have a reasonable possibility of relatedness to the study drug

The IMC will make recommendations as to the further conduct of the study as outlined in the IMC Charter. Other specific operational details such as the IMC's composition, frequency and timing of meetings, and members' roles and responsibilities will be detailed in the IMC Charter. Cohorts evaluating regimens with AT-527 doses lower than 550 mg BID will not require additional IMC oversight.

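### In Cohorts B–D above 550 mg BID, the only rate-based pause rule counts placebo patients in its denominator, so at the unblinded 20-patient review 4 of 15 AT-527 patients with related Grade 3/4 events do not mandate a pause

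*Protocol*

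**What the plan says.** Protocol 3.1 gives the IMC three reasons to pause enrolment: one related death, one related life-threatening SAE, and a rate criterion, met when ">20% of the enrolled patients in any cohort experience clinically significant Grade 3 or 4 adverse events" judged related by the investigator. The Synopsis repeats it. SAP 1.2.2 has the same rule ("Greater than 20% of the enrolled patients in any cohort experience clinically significant Grade 3 or 4 AEs"), although that section still describes Cohorts B–E.

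The IMC covers cohorts among B–D that test doses above 550 mg BID. Protocol 3.1 states that "the IMC will review safety data through Day 10 for the first 20 patients enrolled in those cohorts". Dose decisions for the next cohort follow its unblinded review, held "after 20 patients (approximately 15 active and 5 placebo) enrolled in the previous cohort have completed assessments through Day 10". Protocol 4.2.2 confirms the access: the roles that may see individual assignments include "operational assay group personnel, IxRS service provider, and IMC members".

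Nothing limits the rate criterion to patients on AT-527 or adds a comparison between arms. The text does not say when the percentage is evaluated, or whether the denominator is the 20 reviewed patients or everyone enrolled by then. IMC recommendations follow a charter that is not among the documents.

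**The concern.** A pooled denominator makes sense for people who cannot see the arms. At this review the IMC can see them, so diluting an AT-527 signal with placebo patients protects nothing.

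The rule matters most for related Grade 3 events that are not life-threatening, because these reach neither of the other two criteria. It applies at doses above 550 mg BID, up to 1100 mg BID, a dose that Protocol 1.3 says had not been given to humans before. If such events cluster on AT-527, the written commitment to pause should respond to the rate on AT-527. As worded, four affected AT-527 patients at the review leave the response to committee judgement.

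**Working it through.** **Inputs.** Threshold strictly above 20% of enrolled patients; 3:1 allocation; review of 20 patients (all Protocol 3.1). The documents give no event rates, so those below are assumptions.

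**The plan's own figure.** 20 × 3/4 = 15 and 20 × 1/4 = 5, which matches the stated split.

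**Trigger counts.** Take the smallest whole number r with r/n > 0.20.
- n = 20: 4/20 = 20.0% does not exceed 20%; 5/20 = 25% does. The rule needs 5 patients.
- With no related placebo event, 4/15 = 26.7% of the AT-527 arm does not trigger; 5/15 = 33.3% does.
- If the denominator is everyone enrolled by the time 20 patients reach Day 10, the count stays at 5 up to 24 enrolled, becomes 6 at 25, and reaches 9 at 40 (9/30 = 30% of the AT-527 arm).

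Related placebo events count toward the 5. They can occur, because Protocol 5.3.4 sets the default: "An adverse event will be considered related, unless it fulfills the criteria specified below".

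**Chance of a pause at the review.** Let A ~ Bin(15, pA) be affected AT-527 patients and B ~ Bin(5, pB) affected placebo patients.
- Current rule: P(A + B ≥ 5).
- Current rule plus a fixed count of 4 on AT-527: P(A + B ≥ 5 or A ≥ 4).

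At a 15/5 split the two differ in one outcome only, A = 4 with B = 0. The gain is therefore P(A = 4) × (1 − pB)^5.

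P(A = 4) is 0.219 at pA = 0.30, 0.225 at 0.25 and 0.043 at 0.10. The factor (1 − pB)^5 is 1, 0.774 and 0.590 for pB = 0, 0.05 and 0.10.

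| True AT-527 rate | Placebo rate | Current rule | With added count |
|---|---|---|---|
| 30% | 0% | 48% | 70% |
| 30% | 5% | 54% | 71% |
| 30% | 10% | 59% | 72% |
| 25% | 0% | 31% | 54% |
| 25% | 5% | 37% | 54% |
| 25% | 10% | 43% | 56% |
| 10% | 0% | 1.3% | 5.6% |
| 10% | 5% | 2.6% | 5.9% |
| 10% | 10% | 4.3% | 6.8% |

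Example, 30% and 10%: 0.589 + 0.219 × 0.590 = 0.718.

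**Why a fixed count.** The split is only approximately 15/5. A bare 20% rule on the AT-527 arm would drop to 3 at a 14/6 split (3/14 = 21.4%) and fire with P(A ≥ 3 | 14, 0.10) = 16% at a true 10% rate. A count of 4 fires 4.4% there.

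**The case against.** The strongest reply is that no decision is shown to change. The IMC sees the arms, dose decisions follow its review, and nothing in Protocol 3.1 confines its recommendations to the three criteria. Shown 4 of 15 against 0 of 5, it could recommend a pause at that meeting, and the charter may already say so. This stands. A reader might infer that such a pattern would pass without action; the documents do not support that. They show only that a pause is not mandatory.

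Second, the gain reflects a lower cutoff: with no placebo events, a pooled cutoff of 4 would also give 70%. True, and the documents name no AT-527 rate the rule was meant to detect. A reader might conclude that 20% is the wrong level, or that an AT-527-only percentage should replace the pooled rule. Neither follows. The level is the sponsor's choice. The pooled count can be followed without unblinding between reviews, and it catches 3 AT-527 plus 2 placebo patients, which an AT-527 count of 4 would miss.

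Third, the timing is open. Checked as patients accrue, 4 of the first 19 (21.1%) would already exceed 20%. Of the equally likely positions of 4 affected patients among 20, 16/20 = 80% place all four in the first 19. Conversely, 25 or more enrolled raises the count needed. So 5 of 20 depends on applying the rule to the reviewed patients, and the point must be read with that condition.

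Fourth, other layers exist: the two single-event triggers, 24-hour SAE reporting and continuous Medical Monitor review. They narrow the gap but set no rate-based pause.

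Fifth, rates of 25–30% have no support in the study so far. At the Cohort A interim at 550 mg BID, "All AEs were Grade 1 or 2 in severity and no SAEs were reported". They are stress cases for higher doses.

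**Conclusion.** The point holds as a modest gap in a mandatory trigger, worth considering for any cohort above 550 mg BID. Applied to the 20 reviewed patients, the pooled rule does not mandate a pause at 4 of 15 on AT-527 with none on placebo. The gap is one patient. Under the assumed rates it is worth about 13 to 23 percentage points of pause probability at true AT-527 rates of 25–30%, and less as related placebo events become more common.

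This rests on a 15/5 split, one evaluation at the review, independent patients, and assumed placebo rates of 0–10%. The figures leave out the single-event triggers, so the overall chance of a pause is higher under either version. How the IMC would act below the threshold cannot be judged without its charter.

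**What to change.** In Protocol 3.1, the Synopsis and SAP 1.2.2, keep the pooled criterion and add a sentence: at its unblinded review, the IMC also pauses enrolment if at least 4 AT-527-dosed patients among those reviewed have related, clinically significant Grade 3 or 4 adverse events, with the placebo count shown beside it. State the trigger as a count, so that an uneven split does not lower it to 3. The same edit could say when the pooled percentage is evaluated and over which patients.

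The cost is wording in three places and one line in the IMC table. No new data are needed, and only staff who are already unblinded need to compute it. The downside is more pauses when the drug is reasonably tolerated: at a true 10% rate, 5.6–6.8% against 1.3–4.3%, an increase of about 2.5 to 4.3 points. A pause starts a safety assessment and does not terminate the study.
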